3.5 Randomization and stratification

We will randomly assign older patients having inguinal hernia surgery to one of the two study arms: (1) local anesthesia or (2) general anesthesia. Our goal for enrollment will be 40 patients in

[figure not shown]

Figure 1. Overview of study design. Patients will be randomized to inguinal hernia surgery under either local or general anesthesia. We will collect baseline characteristics prior to surgery. Intraoperative and immediate postoperative outcomes include time, pain, and cognitive recovery. Post-discharge outcomes include pain, cognitive & physical function, and quality of life. All outcomes collected in-person unless otherwise noted

each arm, equally distributed by site. We will use a stratified randomization scheme with blocking within strata. Stratification factors include hospital location (Dallas or Houston) and age (65-75 or 75+ years). Equal allocation by strata will be used so that differences among hospitals and age groups will be balanced.

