 - Research assistants will contact the patient by phone to complete assessments. This may be completed at any time from 48 hours to 1 week after surgery.
 - Physical function assessment: we will administer the 6-item Katz index to measure independence in activities of daily living
 - Delirium and cognitive assessment: we will administer a battery of tests to assess (1) cognitive function (overall and particular domains including processing, visual scanning, attention, mental set-shifting, executive function, and verbal memory) and (2) delirium risk
 - Confusion Assessment Method (short form)
 - Montreal Cognitive Assessment (5-minute version)
 - Trail Making Tests Parts A and B
 - Pain assessment: we will administer a 10-point visual analog scale to quantify pain levels related to the hernia
 - Quality of life: we will use the 8-item Carolinas Comfort Scale to

- assess hernia-related quality of life
- Adverse events
- Visit 5 (2-Week Postoperative Visit)
 - Our standard clinical practice is to bring patients back to surgery clinic within 2-4 weeks of surgery to assess recovery and evaluate the incision. This assessment can take place any time in that 2-4 week postoperative period.
 - Vital signs
 - Physical function assessment: we will administer the 6-item Katz index to measure independence in activities of daily living
 - Delirium and cognitive assessment: we will administer a battery of tests to assess (1) cognitive function (overall and particular domains including processing, visual scanning, attention, mental set-shifting, executive function, and verbal memory) and (2) delirium risk
 - Confusion Assessment Method (short form)
 - Montreal Cognitive Assessment (5-minute version)
 - Trail Making Tests Parts A and B
 - Pain assessment: we will administer a 10-point visual analog scale to quantify pain levels related to the hernia
 - Quality of life: we will use the 8-item Carolinas Comfort Scale to assess hernia-related quality of life
 - Adverse events

Indicate treatment and follow-up visit assessments for each visit. List all measurements and procedures in bulleted format.

Include allowable time window in which evaluations may take place, e.g., study visits must be performed on the weeks indicated in the Schedule of Evaluations $\pm X$ days. The evaluation time window should be as narrow as technically feasible.

For example:

- Visit 3:
 - *Vital Signs*
 - *Treatment Administration Form*
 - *Concomitant Medications*
 - *Adverse Events*

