6.2.4 Completion/Final Evaluation

- The final evaluation/completion visit will be done by phone or video at 6 months after surgery, and can be performed any time from 6-9 months after the operation by research assistants
- Evaluations will include
 - Physical function assessment: we will administer the 6-item Katz index to measure independence in activities of daily living
 - Delirium and cognitive assessment: we will administer a battery of tests to assess (1) cognitive function (overall and particular domains including processing, visual scanning, attention, mental set-shifting, executive function, and verbal memory) and (2) delirium risk
 - Confusion Assessment Method (short form)
 - Montreal Cognitive Assessment (5-minute version)
 - Trail Making Tests Parts A and B
 - Pain assessment: we will administer a 10-point visual analog scale to quantify pain levels related to the hernia
 - Quality of life: we will use the 8-item Carolinas Comfort Scale to assess hernia-related quality of life
 - Adverse events or serious adverse events

List each assessment to be performed at the participant's final visit.

Specify evaluations needed for participants who discontinue study intervention early. Specify potential reasons for early termination. Specify any requirements (e.g., related to monitoring and reporting of adverse experiences) for follow-up on participants once they have stopped using the study intervention.

7 **SAFETY ASSESSMENTS**

Participant safety should be monitored once an individual is enrolled in the study. To assure comprehensive review of potential safety events, include an alphabetical list of expected adverse experiences for each study intervention, criteria for management and modification of the study intervention regimen or participant assessments if an adverse event occurs.

For investigational drug studies the section should identify toxicities that have been seen in previous studies.

7.1 **Specification of Safety Parameters**

Safety is a significant concern for our team. Overall, the risk for both arms is low, but there is potential risk both from surgery and anesthesia. At each study visit, we will actively examine for and inquire about possible adverse and serious adverse events. Specifically, we will monitor for the following to record in the adverse events database for review:

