 - i. Confusion Assessment Method (CAM) short form: The CAM is the most widely used instrument for detection of delirium, with typical sensitivity of 94% and specificity of 89% across multiple studies.²⁶ The instrument is scored on a 7-point scale and we will consider a 0.5 standard deviation difference as the minimal clinically significant difference.²⁴ Items include evaluation of attention, disorganized thinking, and altered levels of consciousness.
 - ii. Montreal Cognitive Assessment (MoCA) 5-minute form: The MoCA is a widely used tool for detection of dementia and other cognitive impairment, and is sensitive when used as a global cognitive screening tool.²⁷ The 5-minute form was developed to (1) reduce the significant time burden of the longer version which typically takes 15 minutes to complete, while (2) maintaining the psychometric advantages of the longer form, and (3) facilitating assessment by

telephone rather than in-person interviews. The instrument evaluates memory/attention, language fluency, orientation, and recall. The 5-minute MoCA has strong correlation with the full version ($r=0.87$), maintains the discrimination of the full version (area under the curve 0.78 versus 0.75 for full version, $p>0.05$), and has strong test-retest validity (intraclass correlation coefficient 0.89).²⁷ Since the 5-minute MoCA was also developed for testing by phone or in person, it meshes with our protocol plans to conduct immediate and long-term follow up by phone. A difference of 3 points is typically considered clinically significant.²⁷

- iii. Trail Making Tests Parts A and B: The Trail Making Test is one of the most popular neuropsychological tests for detecting processing speed, attention, and visual scanning.²⁸ Part A requires participants to draw a line between circles containing numbers, and the circles must be connected in numerical order. Part B is similar, but alternates letters and numbers (1, A, 2, B, et). Both items are scored as time to completion and then normalized to population data based on age and education.²⁸ To address ceiling effects on Part B, we will use the efficiency score for individuals who do not complete the instrument in <300 seconds.²⁹ A 0.5 standard deviation difference in time is considered clinically significant.²⁸
 - b. Timing: All measures will be administered at baseline, prior to discharge, at 48 hours after discharge, at 2 weeks after surgery, and at 6 months after surgery
- 4) Outcome: Pain

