10 DATA COLLECTION AND QUALITY ASSURANCE

10.1 Data Collection Forms

Data will be collected for each participant by a research assistant blinded to the treatment assignment. For the baseline assessment, all forms will be completed after verifying eligibility but before opening the envelope with the treatment assignment. For subsequent assessments, another research assistant not familiar with the patient’s assignment will complete all case report forms. Every case report form will be reviewed, approved, and signed by the site principal investigator and by the project principal investigator.

Case report forms will be provided for each patient and instructions for completion maintained in our Manual of Procedures, which will be given to study staff at each participating site.

Data will be entered into an online, secure REDCap database to help maintain participant confidentiality. Additionally, separate databases will be maintained with (1) participant identifying information and (2) data from case report forms, which will be labeled with the participant’s study number. After entering data into the database, the participant can only be

identified by combining the two datasets. Otherwise, all data entry is guided by the participant's study identification number.

Indicate how information will be collected for each participant and by whom. For example if a blinded observer will perform outcome assessments, state who this person will be. Describe methods for maintaining confidentiality of participant records. Refer to Manual of Procedures (MOP) for description of study forms (also called Case Report Forms).

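### Trail Making A and B, defined as timed drawing tests, are scheduled at phone and phone-or-video contacts with no remote method stated

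*Combined protocol and SAP*

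**What the plan says.** Section 9.4.2 describes the test as a drawing task: "Part A requires participants to draw a line between circles containing numbers". Part B is described as similar, with letters and numbers alternating. On scoring it says: "Both items are scored as time to completion and then normalized to population data based on age and education".

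The timing line for the cognitive battery reads "All measures will be administered at baseline, prior to discharge, at 48 hours after discharge, at 2 weeks after surgery", and goes on to 6 months. The schedule in 6.1 and the visit lists in 6.2.3 and 6.2.4 also place Trail Making at Visit 4 and at 6 months. (They time Visit 4 from surgery, whereas 9.4.2 times it from discharge. I take these to be the same contact.)

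On mode, section 6.2.3 says of Visit 4: "Research assistants will contact the patient by phone to complete assessments". Section 6.2.4 says: "The final evaluation/completion visit will be done by phone or video at 6 months after surgery". Section 7.2.1 also treats the 6-month contact as a phone call when symptoms are elicited.

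Section 9.4.2 addresses phone use for one cognitive test only, the 5-minute MoCA, of which it says "it meshes with our protocol plans to conduct immediate and long-term follow up by phone". Nothing equivalent is said for Trail Making. The Figure 1 caption in 3.5 sets a default: "All outcomes collected in-person unless otherwise noted". For case report forms, section 10.1 refers to "instructions for completion maintained in our Manual of Procedures". That manual is not among the supplied documents.

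**The concern.** On an ordinary phone call the assessor can neither present a sheet of circles nor watch and time the line being drawn. Followed literally, the schedule asks for a score that the stated mode of contact cannot produce. The in-person default in the Figure 1 caption does not resolve this, because 6.2.3 and 6.2.4 note otherwise for exactly these two contacts.

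What is at stake depends on what staff then do.

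- **No score is entered.** The complete-case analysis in 9.5.3 has no Trail Making data at Visit 4, and the chained-equation imputation has no observed values at that visit in either arm. Part of the missing-data proportion, a primary feasibility outcome, then reflects the schedule and not the participants.
- **An altered task is scored.** The missing-data figure looks clean, but the scores are not comparable with the norms or with the drawn baseline. At 6 months, scores obtained in different ways may be combined.

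A pilot whose stated purpose includes testing instruments should not leave this to be settled at the bedside or on the phone.

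**Working it through.** The documents give no power or sample-size figure for Trail Making, so there is nothing of the plan's own to reproduce. The check is a count.

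**Time points.** The post-baseline administrations are before discharge (in person), Visit 4 (phone), 2 weeks (clinic) and 6 months (phone or video). Visit 4 is always affected. The 6-month visit is affected when done by phone, and by video too if no procedure exists. That is 1 of 4 (25%) to 2 of 4 (50%).

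**Scores.** Inputs are 80 participants (9.2.1), with 100% followed to 2 weeks and 90% at 6 months (hypotheses in 9.1.4), so 0.90 × 80 = 72 at 6 months. There are two scores, A and B, per administration.

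- Planned post-baseline scores: 80 × 2 × 3 + 72 × 2 = 480 + 144 = 624.
- Visit 4 only (every 6-month contact by usable video): 80 × 2 = 160; 160/624 = 25.6%.
- Visit 4 plus every 6-month contact by phone: 160 + 144 = 304; 304/624 = 48.7%.

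The lower figure counts every video score as usable, although no video procedure is stated.

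**Contribution to the missing-data outcome if no score is entered.** Section 9.4.1 defines this as missing items over possible items. Item counts come from Table 3 and 6.2.2; treating each trail as one item is my assumption.

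- Baseline: Katz 6 + CAM 4 + MoCA 8 + Trail 2 + pain 1 + Carolinas 8 + FRAIL 5 = 34.
- Visit 3: CAM 4 + MoCA 8 + Trail 2 + pain 1 = 15.
- Visit 4, 2 weeks and 6 months: 6 + 4 + 8 + 2 + 1 + 8 = 29 each.
- Total per fully followed participant: 34 + 15 + 3 × 29 = 136.
- Visit 4 only: 2/136 = 1.5%. Both visits: 4/136 = 2.9%.

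The denominator is uncertain, so I varied it:

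| Items counted | Visit 4 only | Both visits |
|---|---|---|
| 124 (without Katz at Visit 4, pain at Visit 3 and FRAIL) | 2/124 = 1.6% | 4/124 = 3.2% |
| 136 | 1.5% | 2.9% |
| 191 (adds 11 satisfaction items at 5 visits) | 2/191 = 1.0% | 4/191 = 2.1% |

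All are below 5%. Because the metric pools all instruments, the target could be met while 1 or 2 of the 5 Trail Making administrations (20% to 40%) are absent. If an altered task is scored instead, the addition to the metric is 0%.

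**The case against.** The strongest reply is that administration detail belongs in the Manual of Procedures. Section 10.3.1.2 trains research assistants on that manual and on giving every instrument. Participants are seen in person at baseline and before discharge, and section 4.3.4 collects postal and email addresses, so a form could be handed over or sent ahead, drawn at home and returned. The pain visual analog scale is also scheduled by phone without a stated method, which suggests a general choice about level of detail. This stands as a limit: a reader might infer that the remote scores are certain to be lost, and the documents do not support that. It does not remove the point, because the protocol schedules a drawn, normed test by phone and neither states nor cites a way to do it.

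It is also fair to say that the harm is modest. The outcome is exploratory, and Trail Making is one of three cognitive measures. Section 9.5.2 plans no change-from-baseline analysis. If everyone took the same altered task at Visit 4, a between-arm rank-sum test on raw scores would still be possible. Missing data are reviewed every two weeks, so a total absence at Visit 4 would be noticed early. All of this stands and bears on priority.

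A reader might further infer that mixing phone and video scores at 6 months would inflate the standard deviation and enlarge the next trial. The documents do not support this. Section 9.4.2 sets the important difference as 0.5 SD, so the standardised effect stays at 0.5 whichever SD is used: 2 × (1.960 + 0.842)² / 0.5² = 62.8, or 63 per arm at 80% power and two-sided 5%. The documents also give no phone share and no size for any mode shift, and 9.1.4 leaves the next trial's primary outcome open.

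**Conclusion.** The point holds conditionally. The schedule and the test definition conflict within the protocol. Unless the Manual of Procedures supplies a remote method, the defined score cannot be obtained at Visit 4 or at any 6-month phone contact: 160 to 304 of 624 planned post-baseline scores (25.6% to 48.7%). This assumes the plan's own retention hypotheses and counts video as usable.

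If those scores are left missing, they add about 1.5% to 2.9% of items to the missing-data outcome under the assumed 136-item count (1.0% to 3.2% over the denominators tried). A reader might infer that the <5% target fails; on these figures it does not fail from this cause alone. If an altered task is scored instead, the loss is comparability with the norms and with the drawn baseline.

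Baseline, pre-discharge and 2-week scores are unaffected. The protocol should be corrected before enrollment, but the pilot's main conclusions do not depend on it.

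**What to change.** In 6.1, 6.2.3, 6.2.4 and the 9.4.2 timing line, schedule Trail Making A and B only at the in-person visits: baseline, before discharge and 2 weeks. Keep the test at 6 months only if one observed, timed procedure is set for all participants, for example video with a form supplied in advance, and record the mode. Otherwise drop it at 6 months, so that collection does not depend on who happens to use video.

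At contacts where the test is not scheduled, use a separate code instead of -99 and exclude those items from the missing-data denominator in 9.4.1. Report Trail Making completion by visit as its own line so that the loss stays visible. Amend the cognitive domain lists for Visit 4 (6.2.3) and 6 months (6.2.4) to match what is still measured.

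If the Manual already holds a remote version, cite it in 9.4.2. If the task differs from the drawn test, do not norm those scores or pool them with the drawn ones.

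The cost is protocol wording and one database code, or a cross-reference if the Manual already covers it. The real loss is that processing speed, visual scanning and set-shifting go unmeasured at phone contacts; the 5-minute MoCA covers memory and attention, language fluency, orientation and recall, and does not replace them. Keeping them at 6 months by video adds participant burden.

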6.2.4 Completion/Final Evaluation

- The final evaluation/completion visit will be done by phone or video at 6 months after surgery, and can be performed any time from 6-9 months after the operation by research assistants
- Evaluations will include
 - Physical function assessment: we will administer the 6-item Katz index to measure independence in activities of daily living
 - Delirium and cognitive assessment: we will administer a battery of tests to assess (1) cognitive function (overall and particular domains including processing, visual scanning, attention, mental set-shifting, executive function, and verbal memory) and (2) delirium risk
 - Confusion Assessment Method (short form)
 - Montreal Cognitive Assessment (5-minute version)
 - Trail Making Tests Parts A and B
 - Pain assessment: we will administer a 10-point visual analog scale to quantify pain levels related to the hernia
 - Quality of life: we will use the 8-item Carolinas Comfort Scale to assess hernia-related quality of life
 - Adverse events or serious adverse events

List each assessment to be performed at the participant's final visit.

Specify evaluations needed for participants who discontinue study intervention early. Specify potential reasons for early termination. Specify any requirements (e.g., related to monitoring and reporting of adverse experiences) for follow-up on participants once they have stopped using the study intervention.

7 **SAFETY ASSESSMENTS**

Participant safety should be monitored once an individual is enrolled in the study. To assure comprehensive review of potential safety events, include an alphabetical list of expected adverse experiences for each study intervention, criteria for management and modification of the study intervention regimen or participant assessments if an adverse event occurs.

For investigational drug studies the section should identify toxicities that have been seen in previous studies.

7.1 **Specification of Safety Parameters**

Safety is a significant concern for our team. Overall, the risk for both arms is low, but there is potential risk both from surgery and anesthesia. At each study visit, we will actively examine for and inquire about possible adverse and serious adverse events. Specifically, we will monitor for the following to record in the adverse events database for review:

7.1.1 Definition of adverse events (AE)

Adverse event means any untoward medical occurrence associated with the use of an intervention in humans, whether or not considered intervention-related (21 CFR 312.32(a)).

7.1.2 Definition of serious adverse events (SAE)

A SAE is any event that results in death, a life-threatening adverse event, inpatient hospitalization or prolongation of existing hospitalization, a persistent or significant incapacity or substantial disruption of the ability to conduct normal life functions, or a congenital anomaly/birth defect. Important medical events that may not result in death, be life-threatening, or require hospitalization may be considered serious when appropriate medical judgement indicates they may jeopardize the patient and may require medical or surgical interventions to prevent outcomes listed in this definition.

7.1.3 Definition of unanticipated problems (UP)

Unanticipated problems involving risks to participants or others include any incident, experience, or outcome that meets all of the following criteria:

- Unexpected in terms of nature, severity, or frequency, given (1) the research procedures that are described in the protocol-related documents (IRB protocol or informed consent), and (2) the characteristics of the patients being studied
- Related or possibly related to participation in the research, where “possibly related” means there is a reasonable probability that the incident, experience, or outcome may have been caused by the research procedures
- Suggests the research places participants (or others) at a greater risk of physical, psychological, economic, social, or other harm than was previously known or recognized

7.1.4 SAE/AE potentially occurring with either local or general anesthesia

- Allergic reaction: if patients develop hives (raised red lesions) or a significant and persistent rash after administration of local or general anesthesia, this will be managed per the usual hospital protocol. Patients will receive a combination of epinephrine, corticosteroids, and antihistamines. Any patient with an allergic reaction will also be admitted for 24 hour observation that includes monitoring of vital signs, and blood pressure support with intravenous fluids. If the allergic reaction occurs during the operation, then the surgery will be canceled along with all assessments and will be rescheduled after it is determined that the operation can be performed safely without the allergic reaction.
- Hematoma or seroma: a collection of fluid in the tissues over the incision site or in the scrotum that is detected on physical exam constitutes either a seroma or hematoma. If minimal symptoms present, this will be managed by observation. If persistent and significant symptoms occur, the seroma/hematoma will initially be managed by aspiration under local anesthesia up to two times. If the symptoms persist after aspiration, then the patient can be taken back to the operating room for surgical evacuation.
- Infection: we define postoperative infections according to the National Surgical Quality Improvement Program definitions of superficial, deep, or organ space.¹⁶ Infections will be managed by obtaining source control via opening the wound

and providing 10 days of oral antibiotics for infections not involving surgical mesh. If infections involve the mesh, then oral or intravenous antibiotics and may be attempted at the discretion of the attending surgeon versus mesh explantation.

- Injury to vessel: during dissection and/or mesh placement, there is the possibility of injury to the femoral or inferior epigastric vessels. If bleeding occurs at these vessels that cannot be resolved by applying pressure, this will be categorized as vascular injury. The inferior epigastric vessel is typically ligated without consequence if injured. Injury to femoral vessels will result in consult to vascular surgery for repair.
- Neuralgia/chronic pain: if patients experience pain at/near the site of surgery for >3 months after the operation, they are considered to have neuralgia. This will be managed initially by consultation with the pain service for injection of steroids and local anesthetic at the site for up to 3 times. If this proves unsuccessful, the patient will be considered for surgical neurectomy.
- Spermatic cord injury or orchitis: during surgical repair, the spermatic cord (including vas deferens, spermatic artery, venous plexus) are mobilized away from the hernia sac. If the surgeon identifies injury (division of the vas deferens, bleeding from artery or veins that requires intervention beyond holding pressure) or if there is involution of the testicle on the side of the surgery (identified by pain beyond the ordinary, swelling in the groin, ultrasound showing no flow) then we will categorize as a spermatic cord injury. Intraoperatively, a vas deferens injury will result in consultation of urology for repair. Arterial and venous injuries are generally too small to repair intraoperatively, but vascular surgery service can be consulted for evaluation. Postoperatively, there is no treatment for cord injury other than pain control, urologic evaluation, and possible removal of testicle on the injured side.
- Thromboembolic event: if patients develop deep venous thrombosis or pulmonary embolism from surgery, the diagnosis will be confirmed by the appropriate imaging tests (typically lower extremity ultrasound and CT of the chest) and treatment with anticoagulation (therapeutic heparin or Lovenox) will be immediately started. Patients will be admitted until they are clinically stable, and we will transition the patient to oral anticoagulation as soon as clinically feasible and arrange for evaluation by the hematology service for long-term follow-up and treatment. Additionally, any supportive care (oxygen, intravenous fluids, medications to support blood pressure) will be provided at the discretion of the treating team. Similarly, myocardial infarction and cerebrovascular accident will be treated by consulting specialists (cardiology or neurology) per the usual hospital protocol. These include anticoagulation and antiplatelet agents along with supportive care. Unless the patient becomes unable to complete study assessments, these complications would not result in changing the study schedule. If patients are unable to complete assessments during the specified time points, then that information would be missing for their records.

